4.2.5. Recruitment of convalescent donors

The recruitment of donors will be carried out by the Hospital Transfusion Services, the Son Llàtzer University Hospital and the Blood and Tissue Bank of the Balearic Islands. Donors will be identified using local, regional or national registries of cured COVID-19 patients. It is also foreseen the recruitment in the family environment of these patients, that is, to study if in the environment of the donor patient there was any other possible donor who met the criteria of inclusion and exclusion, and who after being informed decides to participate voluntarily.

The selection of donors will have several phases:

1. Telephone pre-selection. The donor candidate will be contacted by telephone, informed of the objectives of the study, and if interested, an interview will be conducted to assess whether he meets the selection criteria as a plasma donor and those specific to this trial. Those who meet criteria will be called for a face-to-face appointment.

Alternatively, participation in the study will be proposed upon discharge of the patient by his doctor.

2. First appointment and extraction of analytics.

to. The donor will fill in the usual blood donor form and the pre-selection form for the trial.

b. You will receive the patient information document and sign the informed consent of the trial.

c. The use of the standard blood donor form does not mean that this procedure can be considered a regular plasma donation. These donors must NOT be registered in the plasma donor circuit of the Transfusion Centres.

d. The following samples shall be taken from you:

- Nasal and pharyngeal smear for RT-PCR of Coronavirus SARS-CoV-2.
- Serum sample 6 ml for the quantitative determination of antibodies against Coronavirus SARS CoV-2.

ii. EDTA tube 5 ml for determination of anti-SARS-CoV-19 antibodies

iii. Usual tubes for performing microbiological and immunohematology determinations typical of a regular blood donor.

iv. EDTA tube for blood count.

and. An appointment will be given for plasmapheresis, considering that the microbiological results, both general blood donor and SARS-CoV-2 specific, must be checked and correct.

3. Confirmation call, When the Extraction Centre has all the results, the donor is called to confirm their appointment for plasma extraction. Donors who do not meet any of the analytical requirements will be informed and discarded.

4.2.6. Plasmapheresis of ex-convalescent donors

1. On the day of the appointment, a confirmation will be made that the selection criteria have not changed, and it will be confirmed that the analytical tests are correct.

2. Blood pressure, temperature and heart rate will be taken. Donors with a temperature greater than 37.0°C will not be accepted. Hyper/hypotensive, tachycardia or bradycardia donors will be accepted at the discretion of the Haematologist responsible for the extraction.

3. The donation will be assigned a SIN (Single identification Number; or number of donation).

4. Each of the extraction bags and the documentation related to this donation will be labelled with this NUMBER WITHOUT.

5. An extraction of 600 mL of plasma without leukocytes (< 1 x 10⁶ leukocytes per unit extracted) shall be carried out using any apheresis machine with its corresponding validated sets or kits (CE Marking) for the extraction of plasma for transfusion use. The specific protocol of each commercial house will be used.

Due to the new orders of the Ministry of Health, the Blood and Tissue Bank of the Balearic Islands will be in charge of the treatment of the sample (inactivation, classification, plasmapheresis and sending to the relevant centre). This institution is responsible for generating a plasma bank with anti-SARS-CoV2 antibodies from ex-convalescent COVID-19 donors. These donors will be selected by the Blood and Tissue Bank of the Balearic Islands as Son Llàtzer University Hospital, who will make the extractions and send the sample for treatment to the Blood and Tissue Bank. The apheresis product obtained in Son Llàtzer University Hospital shall be used as a priority in Son Llàtzer University Hospital. For the rest of the participating centres, apheresis products from the plasma bank of the blood and tissue bank will be used.

4.2.7 Processing of plasma units

(IMPORTANT: the rules of the document *RECOMMENDATIONS FOR OBTAINING PLASMA FROM CONVALESCENT DONORS OF COVID-19* of the Ministries of Health will be followed[24])

1. The plasma units (identified with the SIN) will be stored at 20°C (butanediol plates, or similar) if they are to be processed before 8h; or frozen (< -20°C) if they are going to be processed after 8h.
2. Before the pathogen inactivation process, the 600 mL units shall be separated into two 300 mL bags; using sin as traceability. Each of the 300 mL bags is labelled with the SIN followed by subcode 01 and 02.
3. The 300 mL bags shall be subjected to a pathogen reduction process (inactivation), using any pathogen inactivation system validated for the treatment of plasma for transfusion use. The inactivation process will be carried out in accordance with the specific procedures of each commercial house.
4. If the plasma has been previously frozen, it shall be thawed, inactivated and re-frozen within a period of not less than 2h.
5. All processes, from plasma extraction to final storage after inactivation, shall be carried out maintaining a closed system to ensure the sterility of the product, using a sterile tube connection system, validated for the use of transfusion products. Handling of products within a flow chamber as a closed system is not accepted.

-Labelling of plasma units of convalescent donors

1. Inactivated units will be labelled using the SIN code and subcode 01 or 02.
2. The labelling of devices shall preferably follow the criteria set out in the ISBT128 coding of blood products. The labels will include all the information required for any blood product according to the European guidelines¹.
3. Product coding will ideally be done by assigning a new ISBT128 product code that identifies plasma units as specific from COVID19 convalescent donors. The product codes will be:
 - E9746 = Apheresis CONVALESCENT PLASMA| NS/XX/<=-25C| Riboflavin-treated| COVID-19
4. In addition, the labels shall include the following information specific to that investigation product:
PLASMA FROM ALTRUISTIC DONORS CONVALESCING FROM COVID-19
INVESTIGATIONAL PRODUCT FOR USE EXCLUSIVELY WITHIN THE CONPLAS-19
CLINICAL TRIAL
SARS-CoV-2 RNA PCR NEGATIVE; SARS-CoV-2 IgG POSITIVE
STORAGE AND DISTRIBUTION OF PLASMA UNITS FROM CONVALESCENT DONORS
Plasma units will be stored and transported following European indications (up to 36 months at a temperature of -80°C or 3 months between -18°C and -25°C). During transport, it will be ensured that the plasma is kept frozen until its delivery to the receiving centre.

4.2.8. Transfusion of plasma units from convalescent donors

The transfusion procedure will follow the requirements established for any transfusion within the usual clinical practice, ensuring ABO compatibility and always being carried out under the structure of a hospital Transfusion Service and under the supervision of a specialist in Haematology and Hemotherapy. The usual traceability records will be maintained using the computer transfusion management systems available in the Transfusion Services, or alternatively using a specific computer system for the management of the units of this clinical trial.

The adverse effects associated with the infusion of the plasma units of this research study will be recorded following a Hemovigilance procedure with follow-up of the transfusion until 24h after the transfusion (See attached annex, included in the Safety section of this EC).

4.2.9. Adverse events

4.2.9.1. Monitoring and recording of adverse events.

An adverse event (AA) is any harmful, unintended, or unfavourable medical event that occurs or worsens in a patient over the course of a study. It may be a new concurrent disease, the worsening of a concomitant disease, an injury, or any concomitant deterioration of the patient's state of health, including its analytical results regardless of its cause. Any worsening (i.e., any adverse and clinically significant variation in the frequency or intensity of an ailment that was present prior to study treatment) should be considered an AA. The diagnosis or syndrome is recorded in the Data Collection Notebook (CRD).

The investigator must record all non-serious and severe AAs related to the study treatment that occur from the signing of the informed consent up to 30 days after the last dose of the investigational treatment. Severe AA (AAG) that occurs after the signing of the informed consent but before initiating treatment should also be recorded.

The assessment of the AA will include the following aspects:

- Gravity: An AAG is all AA that https://correu.ssib.es/owa/-_msocom_1 :

1. Deathrolls.
2. Threaten life (an AA that, in the opinion of the investigator, carries an immediate risk of death).
3. Hospitalization or prolongation of hospitalization is necessary (hospitalization is defined as a hospital admission, regardless of the length of stay). Scheduled hospitalization, for socio-sanitary reasons or, for this study, that derived from COVID-19, will not be considered an AAG.
4. Persistent or significant disability or disability (substantial impairment of the patient's ability to perform normal activities).
5. Give rise to a congenital anomaly or birth defect.
6. It is an important medical event.

-Severity: The severity/intensity of adverse events (AA) is classified based on the patient's symptoms according to the current version of the toxicity criteria common for adverse events (CTCAE, Version 5.0);

https://ctep.cancer.gov/protocoldevelopment/electronic_applications/docs/CTCAE_v5_Quick_Reference_5x7.pdf

- Causal relationship: The relationship will be defined as **suspicious** in a situation where there is a reasonable possibility that the administration of the investigational medicinal product caused the adverse event. When there is a remote or low probability that the event is related to the study drug then the relationship will be defined as non-suspicious.

-Duration: The start and end dates of the AA must be determined.

- Measures adopted: The actions carried out as a result of the AA and in reference to the study treatment must be indicated. Concomitant treatment should also be recorded if concomitant treatment is required.
- Outcome: The researcher will communicate the outcome of the events, whether it is an AA or an AAG (total recovery, recovery with sequelae, fatal, not recovered / continuous).

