4.2.9.2. Reporting of adverse events

The sponsor or designated person is responsible for reporting the AAG to the Research Ethics Committee and for providing it with all relevant initial and follow-up information about the event. The researcher must keep a copy of all AAG information in his or her file, including correspondence with the sponsor and the Research Ethics Committee.

The researcher must keep copies of all AAG information in a file, including correspondence with the sponsor.

The sponsor or designated person shall notify the relevant Authorities of all relevant and unexpected information on AAG suspected of being related to the study medication, causing death or threatening life, as soon as possible and in any case within a maximum period of seven days of becoming aware of them. Relevant follow-up information on these cases will be notified subsequently, within an additional eight days.

Any other serious and unexpected event suspected to be related to the study medication, as soon as possible, but within a maximum period of fifteen days after the investigator becomes aware of them. The researcher should keep a copy of all relevant security information in his or her file.

-Contact details of the promoter (coincides with the fact that he will be the person in charge of communicating the AA):

[name]

Son Llàtzer University Hospital, Internal Medicine Service

[contact]

[contact], [name]

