		2	Past infection
		3	Immunized
		4	Negative
CMV Serology		0	Negative
		1	Positive
Syphilis Serology		0	Negative
		1	Positive
INMHEMATOLOGIC STUDY			
ABO Blood Group		0	A
		1	B
		2	AB
		3	O
Rh		0	Present
		1	Absent
Irregular Blood Group antibodies		0	Negative
		1	Positive
DIAGNOSTIC/MICROBIOLOGICAL PROCEDURES			
Quantitative titration of SARS-COV2 antibodies (IgG/IgM)		UA/mL	Number
RT-PCR SARS-COV-2		0	Negative
		1	Positive

Time to RT-PCR negativization	Days		Number
CLINICAL CRITERIA			
Pleural effusion		0	Negative
		1	Positive
PSI score		1	Valuation not required
		2	<=70
		3	71 - 90
		4	91 - 130
		5	>130
WHO Progression Scale		0	Uninfected; no viral RNA detection.
		1	Asymptomatic; viral RNA detection
		2	Symptomatic. Independent
		3	Symptomatic. Need for assistance
		4	Hospitalized. Oxygen-free
		5	Hospitalized. Oxygen with mask or nasal tips
		6	Hospitalized. Oxygen by non-invasive ventilation (NIV) or high flow.
		7	Intubation or mechanical ventilation. PO2/FIO2>= 150; or SpO2/FO2> 200
		8	Mechanical ventilation (pO2/FIO2< 150, or SpO2/FIO2< 200), or vasopressor (norepinephrine >0.3 microg/Kg/min)
		9	Mechanical ventilation (pO2/FIO2< 150, or SpO2/FIO2< 200), or vasopressor (norepinephrine >0.3 microg/Kg/min) o dialysis o ECMO
% of patients requiring ICU admission			Number
15-day mortality rate			Number
Mortality rate at 30 days			Number
Days of hospitalization			Number
SECURITY CRITERIA			
Emerging adverse effects (ASD) \geq GIII		0	No
		1	Yes
Type TEAE SPECIFY			Name
Cumulative rate/incidence of ASD \geq GIII in experimental branch			Number

Cumulative rate/incidence of emerging adverse events (ASD) any grade in experimental branch			Number
Hospital discharge date			Date
Exitus		0	Yes
		1	No

Table 1. Variables that will be included in the database of the study.

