Annex V. COLLECTION OF ADVERSE EVENT DATA FOR RESEARCH PRODUCTS

COLLECTION OF ADVERSE EVENT DATA FOR RESEARCH PRODUCTS

Nº CENTER: PROJECT CODE (SPONSOR) :	PATIENT NUMBER: INITIAL TRACKING:	TYPE OF REPORT: RANDOMIZATION:
SPONSOR ID:	CASE ID: DATE OF NOTIFICATION:	DATE OF NOTIFICATION:

I-ADVERSE EVENT INFORMATION.

COUNTRY	DATE OF BIRTH	AGE	SEX	WEIGHT	HEIGHT	SAE START DATE:	

CRITERION OF SERIOUSNESS	SAE END DATE
DEATH	FATAL/ Date of death:
LIFE-THREATENING:	RESOLVED:
HOSPITALIZATION/PROLONGATION IN ALREADY HOSPITALIZED PATIENT:	SOLVED WITH SEQUELS:
SIGNIFICANT OR PERMANENT DISABILITY:	IMPROVING:
CONGENITAL ALTERATION:	PERSISTING:
CLINICALLY SIGNIFICANT	WORSENED:
TRANSMISSION OF INFECTIOUS DISEASE BY A MEDICAL DEVICE:	UNKNOWN:

II-RELEVANT INFORMATION OF THE STUDY PROCEDURE

DATE	START TIME	END TIME	DOSE

ACTION TAKEN REGARDING THE STUDY PROCEDURE			
DOSE REDUCTION	START DATE:	END DATE:	CONTINUOUS:

TEMPORARILY INTERRUPTED	START DATE	END DATE:	CONTINUOUS:
PERMANENT INTERRUPTION	START DATE	END DATE:	CONTINUOUS:

HAS THE INTENSITY OF THE EVENT DECREASED DUE TO THE ACTION TAKEN WITH RESPECT TO THE STUDY PROCEDURE?

HAS THE EVENT REAPPEARED AFTER REINTRODUCING THE STUDY PROCEDURE?

DESCRIPTION OF THE ADVERSE EVENT:
EVENT:
SEVERITY: GRADE 1 GRADE 2 GRADE 3 GRADE 4
DESCRIPTION:

POSSIBLE CAUSE OF THE ADVERSE EVENT
PREVIOUS ILLNESS:
STUDY TREATMENT:
OTHER TREATMENTS:
PROTOCOL-RELATED PROCEDURE
OTHER (SPECIFY):

III- CONCOMITANT MEDICATION AND RELEVANT MEDICAL HISTORY

CONCOMITANT MEDICATION	INDICATION OF USE	FREQUENCY	ROUTE	DOSE	START DATE	END DATE	CONTINUOUS

RELEVANT MEDICAL HISTORY	START DATE:	END DATE	CONTINUOUS

RELEVANT MEDICAL TESTS/PROCESSES	RESULT (UNITS)	NORMAL RANGE	DATE OF THE TEST/PROCEDURE

SAE-SPECIFIC MEDICATION	FREQUENCY	ROUTE	DOSE	START DATE	END DATE	CONTINUOUS

IV-INFORMATION ABOUT THE RESEARCHER:

NAME OF THE RESEARCHER	ADDRESS OF THE RESEARCHER	REPORTED BY:	DATE:	SIGNATURE OF THE RESEARCHER	DATE:

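### The adverse-event passages conflict on whether all events or only treatment-related ones are recorded, and in which arm, so the planned safety comparison depends on which text a centre follows

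*Combined protocol and SAP*

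**What the plan says.** The recording sentence in section 4.2.9.1 reads "The investigator must record all non-serious and severe AAs related to the study treatment". The period runs from consent "up to 30 days after the last dose of the investigational treatment". One addition follows: "Severe AA (AAG) that occurs after the signing of the informed consent but before initiating treatment should also be recorded".

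The same section defines an AE as any unfavourable medical event, "including its analytical results regardless of its cause", and says without any causality condition that the diagnosis or syndrome goes into the data collection notebook. It also keeps a class for events with only a remote chance of being caused by the product: "then the relationship will be defined as non-suspicious".

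Elsewhere:
- Section 3.2.2 makes safety and tolerance, compared with standard treatment, secondary objectives.
- Section 4.2.9.2: "The sponsor or designated person is responsible for reporting the AAG to the Research Ethics Committee". No relatedness condition is attached; that condition appears only in the later sentences on notifying the authorities.
- Table 3 in section 4.3.1, introduced as covering control and treatment groups, has an AE review row.
- Table 1 in section 4.3.3 lists a patient-level yes/no variable for events of grade III or higher, with no arm named. It then lists two cumulative rates, both for one arm; the second is "Cumulative rate/incidence of emerging adverse events (ASD) any grade in experimental branch".
- Annex V has a block headed "POSSIBLE CAUSE OF THE ADVERSE EVENT", with entries for previous illness and other treatments as well as study treatment.
- Section 4.3.2 sets follow-up at 21 days, extended only where necessary. Table 1 also lists mortality at 15 and 30 days.

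**The concern.** A between-arm safety comparison needs the same events collected by the same rule over the same period in both arms. The sentence that states the investigator's duty does not give that. A control patient receives no plasma, so has nothing for an event to be related to and no final dose to close the window. In the plasma arm, whether an event is recorded depends on a causality judgement by staff who know the allocation, because the trial is open-label.

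The surrounding text describes something different: collection in both arms with causality as a descriptor. Several centres take part, and each could reasonably follow a different sentence. Control events that are never entered may not be recoverable at analysis.

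The secondary issue is late follow-up. The recording duty, and possibly the 30-day mortality outcome, extend past the last planned contact, so serious events and deaths after discharge may be missed.

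**Working it through.** The plan states no AE rate or sample size, so there is no figure to reproduce. The check has two parts.

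**1. The texts side by side**

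| Place | Causality filter | Arms |
|---|---|---|
| 4.2.9.1, recording sentence | related only | none named; window tied to the plasma dose |
| 4.2.9.1, addition | none (serious, before treatment) | none named |
| 4.2.9.1, definition and notebook sentence | none | none named |
| 4.2.9.1, causality classes | keeps unrelated events | none named |
| 4.2.9.2, ethics committee | none | none named |
| Table 3, AE review | none | both |
| Table 1, grade III or higher variable | none | none named |
| Table 1, cumulative rates | none | experimental only (2 of 2) |
| Annex V, cause fields | includes other causes | none named |

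The addition for serious events before treatment has work to do only if the preceding sentence is restrictive. The unrelated class has work to do only if unrelated events are recorded. Both stand in the same section, and neither that section nor section 5 says which prevails.

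- *Related-only sentence followed:* after baseline, control recording is close to empty, while plasma-arm recording equals whatever is attributed to plasma. Control events are under-recorded relative to plasma.
- *Any-cause text followed:* AE review exists in both arms at 7 time points (screening and days 1, 2, 3, 7, 14, 21). The grade III or higher variable can be tabulated by arm, and 15-day mortality falls inside scheduled follow-up. A comparison to day 21 is possible.

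**2. Day arithmetic**

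Inputs: infusions on study days 1 and 2 (section 4.1); window of 30 days after the last dose (4.2.9.1); last visit on day 21 with a margin of 24 hours either way, so day 20 to 22 (4.3.1).

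- End of AE window: 2 + 30 = day 32.
- Gap after the last visit: 32 − 21 = 11 days; with the margin, 32 − 22 = 10 to 32 − 20 = 12.
- If only the first infusion is given: 1 + 30 = day 31, a gap of 31 − 21 = 10 days.
- 30-day mortality, assuming study day 1 is the origin: 30 − 21 = 9 days; with the margin, 30 − 22 = 8 to 30 − 20 = 10.
- If the origin were symptom onset and study day 1 fell on symptom day s, the time point would be study day 30 − s + 1. That gives day 30 for s = 1 and day 24 for s = 7. It would reach day 21 only for s of 10 or more.
- AE reviews scheduled after day 21: 0.

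**The case against.** The best case on the other side is that the related-only phrase is loose drafting in a translated text and that any-cause recording was meant throughout. Several details support this. The notebook sentence has no filter. Recording starts at consent, before plasma could cause anything. Hospitalization due to COVID-19 is expressly excluded from serious events, which would hardly be needed if only plasma-related events counted. Section 4.2.8 already gives infusion effects their own 24-hour haemovigilance route, so 4.2.9.1 is more plausibly the general rule. Annex V has a randomization field. Table 1 is captioned as a list of database variables, not as an analysis plan, and a control rate for grade III or higher could be derived from the patient-level variable.

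Most of that stands, and it limits what can be claimed. A reader might infer that the safety comparison is already biased or undefined, or that controls will have no AE data. The documents do not support that: they schedule AE review in controls to day 21 and contain enough any-cause text for a sound comparison to that day. What the objection cannot do is remove the sentence that states the duty. A centre following it as written would be following the protocol, and the addition for pre-treatment serious events favours the restrictive reading. Table 1 also defines no any-grade variable or rate for controls.

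On follow-up, a reader might infer that 30-day mortality cannot be observed. That goes too far. Its origin is not stated, death and discharge date are collected, patients still in hospital remain under observation, and section 4.3.2 permits extension. A recording duty also does not itself require a visit. The remaining gap concerns patients already discharged, for whom a discretionary extension does not assure complete or equal ascertainment.

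**Conclusion.** The AE passages contradict each other on what is recorded and in whom, and should be reconciled. The consequence is conditional: biased or undefined if centres apply the related-only sentence, a usable comparison to day 21 if they apply the rest. The direction under the first reading is clear (controls under-recorded). The size is not, because the documents give no AE rates, arm sizes or attribution shares, and none is claimed here.

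The secondary point is firm for the AE window: 11 days (10 to 12) beyond the last scheduled visit when both infusions are given on days 1 and 2. It is provisional for mortality: 9 days (8 to 10), on the assumption that counting starts at study day 1.

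**What to change.** - Reword the recording sentence in 4.2.9.1 so that every AE is recorded in both arms from consent, whatever its cause, up to one common day counted from assignment. Day 32 would keep roughly the present length. Keep the suspected/not-suspected judgement as an attribute of each event.
- Define the two cumulative AE rates in Table 1 for each arm, so that they can be compared.
- State the time origin of 30-day mortality.
- Add one vital-status and serious-AE check, by record or telephone, at about day 30–32 in both arms. For mortality only, the alternative is to restate the outcome to day 21.

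The cost is an amendment, more AE entries in the data collection notebook (chiefly for controls), and one record check or call per patient.

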4.2. Patient selection

4.2.1. Inclusion criteria

Plasma donors may be selected from among patients already discharged for COVID-19 in the centres participating in the study (who have not received plasma), as well as by volunteers who meet the requirements for inclusion and non-exclusion, who wish to donate and go to HUSLL or the blood and tissue bank of the Balearic Islands.

The study sample for both the intervention and control group will be extracted from patients who are positive in the real time-polymerase chain reaction (RT-PCR) test for the detection of COVID-19, in any of the participating centres (admitted to the plant or ICU), and who meet the inclusion and non-exclusion criteria, and voluntarily wish to participate, after being informed with the Patient Information Sheet (HIP), and have signed the informed consent (IC).

Both donors and study subjects will be provided with the specific HIP and IQ. Each participating centre will sign a participation agreement, confidentiality commitment and transfer of study results for further analysis, following the usual logistics guidelines of multicentre studies.

1. Below are the inclusion criteria:

For the receiver:

A. Recipients hospitalized in COVID-19 floor:

1. Ability to understand the HIP and sign the IQ of the study.
2. Age greater than or equal to 18 years, male or female.
3. Patient hospitalized in COVID-19 floor (or equivalent areas in each centre) with COVID-19 diagnosis by PCR in nasopharyngeal smear or in any other biological sample.

4. Presence of respiratory symptoms and / or fever associated with COVID-19, with time of evolution of the clinic by COVID-19 equal to or less than 7 days (being day 1 the day of onset of symptoms and including day 7).
5. Presence of pneumonia in chest x-ray and/or $\text{SatO}_2 < 94\%$ aa.
6. Sequential Organ Failure Assessment score (SOFA) ≤ 6 .
7. Accept the condition of complying with the procedures established in the protocol.
8. That you will remain admitted at least 5 days at the discretion of the clinician, in order to perform the procedures correctly.

B. Recipients hospitalized in ICU:

1. Ability to understand the HIP and sign the IQ of the study. **In case of impossibility of signing IC (e.g., intubated patients) the oral IC will be accepted.**
2. Age greater than or equal to 18 years, male or female.
3. Patient hospitalized in ICU with COVID-19 diagnosis by PCR in nasopharyngeal smear or in any other biological sample.

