Patients who do not meet the inclusion criteria may remain in conventional hospitalization and should be re-evaluated. Patients who are classified as "red" have priority admission to the ICU, followed by those classified as "yellow". Patients classified as "blue/black" remain in conventional hospitalization and receive palliative care with active medical therapy at the discretion of the attending physician and according to the opinion of the patient and/or family. Patients should be re-evaluated on days 2 and 5 and re-classified. Decisions beyond day 5 in icu will depend on the availability of resources (these criteria are those dictated by the Spanish Society of Intensive Care Medicine (Semicyuc) for ICUs).

For the donor:

1. Ability to understand the HIP and sign the IQ of the study.
2. Age equal to or greater than 18 years.

3. Compliance with the criteria to be accepted as a plasma donor according to European and Spanish regulations (RD 1088/2005).
4. Presence of IgG antibodies **against SARS-CoV-2 delectables in peripheral blood 50 UA/mL.**
5. Absence of COVID-19 symptoms in the last 14 days.
6. NEGATIVE SARS-CoV-2 RT-PCR in at least one nasopharyngeal sample.
7. Weight over 50 kg and good venous access.
8. Acceptance for the conservation of serum library samples for the realization of antigranulocyte antibodies; especially in cases in which the recipient presents respiratory clinic.

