4.2.2 Exclusion criteria

For the receiver:

A. Recipients hospitalized in COVID-19 plant:

1. Patients with a previous history of allergic reaction to any type of transfusion of blood products.
2. Breastfeeding women or women with pregnancy potential and positive pregnancy test.
3. Patients who have been treated with plasma in the 21 days prior to the screening/baseline visit.
4. Patients who, in the opinion of the researcher, possess any condition that makes the recruitment of the same incompatible.
5. Patients who are at the time of the study, participating in a clinical trial.
6. Patients who have not performed all the procedures in the study.

For the donor:

1. Plasmapheresis in the last 7 days.
2. Blood donation in the last 7 days.
3. Donation of more than 25 L of plasma in the previous 12 months.
4. With the intention of reducing the risk of transfusion-related acute lung injury (LPART/TRALI), only male donors never transfused and women with no history of abortions will be selected.

5. Patients who are at the time of the study, participating in a clinical trial.

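### The COVID-19 exemption from serious-event status is not limited to the index admission, so respiratory worsening after plasma that leads only to readmission (or, on a broader reading, a longer stay) can go unreported as serious

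*Combined protocol and SAP*

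**What the plan says.** Section 4.2.9.1 (Gravity) lists six alternative criteria, any one of which makes an adverse event (AA) a serious one (AAG). Item 3 is "Hospitalization or prolongation of hospitalization is necessary", with hospitalization defined as an admission of any length. The same item ends with the exemption: "Scheduled hospitalization, for socio-sanitary reasons or, for this study, that derived from COVID-19, will not be considered an AAG". Items 1 (death), 2 (life-threatening), 4 (disability), 5 (congenital anomaly) and 6 (important medical event) carry no such exemption.

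The same section defines an AA irrespective of cause and counts clinically significant worsening of an existing condition as one. Its recording rule, however, covers serious and non-serious AAs judged related to study treatment, up to 30 days after the last dose. AAGs arising between consent and the start of treatment are also recorded.

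Section 4.2.9.2 has the sponsor report AAGs to the ethics committee, with no causality condition. Authorities are notified only of serious, unexpected events suspected to be related.

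Annex V, the serious-event form, lists "HOSPITALIZATION/PROLONGATION IN ALREADY HOSPITALIZED PATIENT" among its seriousness criteria and has no COVID-19 exemption.

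**The concern.** The protocol anticipates lung injury from plasma. Donor exclusion 4 (4.2.2) begins "With the intention of reducing the risk of transfusion-related acute lung injury (LPART/TRALI", and donor inclusion 8 (4.2.1) provides for stored donor serum to be tested for antigranulocyte antibodies, "especially in cases in which the recipient presents respiratory clinic". Recipients already have respiratory disease when they enter. Ward and ICU patients need respiratory symptoms and/or fever from COVID-19, and ward patients also need "Presence of pneumonia in chest x-ray and/or" low oxygen saturation. When such a patient worsens after an infusion, COVID-19 is nearly always a plausible explanation, and the site making the attribution knows which arm the patient is in (4.1).

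If that attribution also settles whether the event is serious, an imbalance between arms in this kind of worsening could be missing from the reports the ethics committee receives while patients are still being treated. Comparing the safety of the two arms is a stated secondary objective (3.2.2).

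**Working it through.** No arithmetic applies. The plan gives no figure on this point, so the check is to read the sections against one another.

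**Step 1. What the exemption can mean.** Three readings are possible:
- Index only: it covers just the admission during which the patient was enrolled.
- Admissions: it covers any admission put down to COVID-19, because the sentence says hospitalization and item 3 has just defined that as an admission.
- Whole item: it qualifies everything in item 3, including prolongation.

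The first may well be what was meant, but no words say so. The second is the most literal.

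**Step 2. Classify post-infusion respiratory worsening under each reading.** In the first two rows the event meets no seriousness criterion other than item 3.

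| Event | Index only | Admissions | Whole item | Annex V |
|---|---|---|---|---|
| Readmission, attributed to COVID-19 | AAG | not AAG | not AAG | serious |
| Prolonged stay, attributed to COVID-19 | AAG | AAG | not AAG | serious |
| Either event, attributed to plasma | AAG | AAG | AAG | serious |
| Fatal, life-threatening, disabling or judged medically important | AAG | AAG | AAG | serious |

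An event loses AAG status through this sentence only if both conditions hold: item 3 is its sole criterion, and it is judged to come from COVID-19. Within that set, the text and the form can classify the same event differently.

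**Step 3. Can the set contain events?** Yes, for both rows. Every recipient is an inpatient at entry (4.2.1), so item 3 operates through prolongation until discharge. Section 4.3.1 foresees discharge after 7 days with outpatient visits on days 14 and 21, and the recording window runs to 30 days after the last dose, so readmission can fall within follow-up.

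**Step 4. What is lost.** An event attributed to COVID-19 would not reach the authorities in any case, because 4.2.9.2 requires suspicion of a causal link. Ethics committee reporting has no causality condition, so that is the route the exemption removes.

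**Step 5. The recording rule.** An AA is defined irrespective of cause, yet the duty to record is worded for treatment-related AAs. Read literally, an event attributed to COVID-19 need not be recorded at all, even if it meets item 1 or 2. The two statements sit in the same section and do not agree. This second attribution test lies upstream of seriousness, so correcting item 3 alone would not be enough.

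**The case against.** The strongest reply is that the gap is narrow and largely covered elsewhere. Several parts of it stand.

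- **Other criteria apply.** A reader might infer that respiratory worsening put down to COVID-19 can never be serious. The documents do not support that. The exemption sits in item 3 only, and item 6 can capture marked deterioration whatever its cause. Item 6 has no definition or examples, however, so it rests on judgement at the same unblinded site.
- **Prolongation is not exempted by name.** Annex V keeps it as a criterion, which favours a narrow reading. Infusions are given on days 1 and 2, and ward patients are expected to stay at least 5 days, so an acute reaction would normally arise during the stay and act through prolongation. On the narrower readings it would still be an AAG, and on the admissions reading the gap is limited to later readmission. The text appears to be a translation, and the index admission is its natural referent. This limits the size of the problem but does not remove the ambiguity.
- **TRALI is not the only named risk.** A reader of the donor criteria might think so, but allergic reaction to transfusion is a recipient exclusion (4.2.2) and infusion-related reactions appear among the discontinuation criteria (4.2.4). The argument needs only that a pulmonary reaction is hard to distinguish from COVID-19.
- **An excess would not be invisible.** A reader might infer that nobody could see it. The plan has haemovigilance with "follow-up of the transfusion until 24h after the transfusion", adverse-effect review at every visit, and fields for effects of grade III or higher, ICU admission, days in hospital and the WHO progression scale (4.3.3). These could show an excess at final analysis. They do not replace AAG reporting during the trial: haemovigilance covers effects associated with the infusion, which is again an attribution, and the cumulative adverse-effect rates in 4.3.3 are defined for the experimental branch only.

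**Conclusion.** The concern holds in a bounded form. The exemption in item 3 is a stated rule that is not confined to the index admission. It allows an open-label attribution to COVID-19 to take respiratory worsening after plasma out of AAG reporting to the ethics committee when readmission is the only seriousness criterion met or, on the broadest reading, when a prolonged stay is. The text conflicts with Annex V on those events, and the related-only recording rule adds a second attribution test.

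The size can be stated only as a class of events. The documents give no rate of readmission, prolonged stay or transfusion reaction, so no number of missed AAGs can be derived.

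The conclusion assumes that sites apply the sentence as written and that no removed page restricts it. If it was meant for the index admission alone, the remedy is a clarification, and the related-only recording wording still needs correcting. The point should be dealt with because it affects safety reporting during the trial and is cheap to settle. It does not show that the safety data as a whole could not register harm from plasma.

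**What to change.** Amend three places so that they agree.

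1. **4.2.9.1, item 3.** Limit the exemption. For example: *The COVID-19 admission during which the patient was enrolled is not in itself an AAG. Any later prolongation of that stay, and any readmission, is assessed against all six criteria whatever its presumed cause, in both arms.* The exemptions for scheduled and social admissions can stay.
2. **4.2.9.1, recording rule, with 4.2.9.2.** Require AAs to be recorded irrespective of cause, in line with the section's own definition, with causality as a separate field. Apply this to both arms and give controls a date from which to count the 30 days, since the present window runs from the last dose of investigational treatment. State in 4.2.9.2 that ethics committee reporting follows seriousness, not attribution.
3. **Annex V.** Put the same index-admission limit beside the hospitalization/prolongation criterion.

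The cost is amendment wording and some additional AAG forms, many of which will turn out to describe COVID-19 progression. No visit or test is added. It is not necessary to make every rise in respiratory support after an infusion an AAG automatically. Among ICU patients, who enter with SOFA above 6, that could generate many reports of disease progression, and the trade-off is debatable.
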